### 5.3.3. Stopping Criteria

Dosing in the study may be stopped if **three or more** subjects receiving GSK1278863 experience any of the safety criteria listed below. An individual subject may also be withdrawn at the discretion of the Investigator and the GSK Medical Monitor for other safety reasons not listed below.

The subject will be followed at the discretion of the Investigator, and the GSK Medical Monitor will be notified. In the event one or more subjects are withdrawn, additional subjects may be enrolled (upon consultation with the GSK protocol contact, see Section 4.1) to ensure an adequate number of subjects complete the study. For an individual study participant, stopping criteria include, but are not limited to:

- Severe signs or symptoms, or significant changes in any of the safety assessments, that put the safety of the individual at risk (e.g., ECG, vital signs, laboratory tests, etc), as judged by the Investigator in consultation with the Medical Monitor if necessary.
- Pregnancy.
- Active GI bleeding or new diagnosis of peptic or duodenal ulcer disease.
- Diagnosis of cancer, with the exception of squamous cell and basal cell carcinoma.
- Cardiovascular ischemic event or thrombotic events (e.g., myocardial infarction (MI), acute coronary syndrome, stroke, deep venous thrombosis, pulmonary embolism, new onset or worsening limb ischemia) excluding events associated with vascular access.
- New onset or clinically significant worsening right heart failure or right heart strain not explained by fluid intake.
- Treatment emergent pulmonary hypertension, new onset or worsening retinopathy (e.g., proliferative retinopathy or macular edema), or new onset or worsening nontraumatic joint inflammation (e.g., rheumatic or psoriatic arthritis).
- Subjects with new onset or worsening clinically-significant signs or symptoms affecting:
  - a. the gastrointestinal system (e.g., evidence of GI bleeding, new onset positive fecal occult blood test, abdominal pain other than transient, minor abdominal pain, etc.)

- b. vision (e.g., persistent blurred or diminished vision)
  - c. the pulmonary system (e.g., persistent significant dyspnea)
  - d. the musculoskeletal system (e.g., significant myalgias or joint inflammation)
- New onset or clinically significant worsening of hypertension inadequately responsive to change in anti-hypertensive therapy, **OR** BP  $\geq$ 180/110 mmHg (on a study visit day) which persists for >48 h despite optimal treatment.
  - Non-hypertensive subjects with normal baseline blood pressure that experience an increase in blood pressure to  $\geq$  160/100 mmHg that persists over 24 h. Any subject who demonstrates this increase in blood pressure will be followed to resolution, until any antihypertensive therapy is withdrawn.
  - Subjects with stable elevated blood pressure at baseline that further increases above baseline by either >20 mmHg systolic, >10 mmHg diastolic, or achieves  $\geq$  180/110 mmHg. To meet this criterion these elevations must persist longer than 24 h. Any subject who develops worsening hypertension requiring intervention will be followed to resolution, until any intervention therapy is withdrawn.
  - On Days 3, 7 and 11, subject's hemoglobin will be assessed prior to dosing using a HemoCue device. Should subjects have an absolute hemoglobin level > 11.0 g/dL, a second hemoglobin measurement will be obtained at the same study visit to confirm. If confirmed, permanently discontinue GSK1278863 and withdraw subject from the study.
  - On Days 3, 7 and 11, subject's hemoglobin will be assessed prior to dosing using a HemoCue device. Should subjects have an absolute hemoglobin level of <8.5 g/dL, a second hemoglobin measurement will be obtained at the same study visit. If confirmed, permanently discontinue GSK1278863 and withdraw subject from the study.
  - CPK level >5xULN without confirmed alternative etiology or if deemed clinically significant by the Investigator.

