**Safety**

1. A positive test for HIV antibody.
2. Uncontrolled hypertension (diastolic BP  $> 100$  mmHg or systolic BP  $> 170$  mmHg) at Screening.
3. History of drug abuse or dependence within 6 months of the study.
4. History of sensitivity to GSK1278863, or its components thereof or a history of drug or other allergy that, in the opinion of the Investigator or GSK Medical Monitor, contraindicates their participation.
5. History of sensitivity to heparin or heparin-induced thrombocytopenia (if the clinical research unit uses heparin to maintain intravenous cannula patency).

6. History of thrombosis defined as deep vein thrombosis, stroke, pulmonary embolism or other thrombosis related condition within 3 months prior to Screening.
7. History of myocardial infarction or acute coronary syndrome within 3 months prior to Screening.
8. History of stroke or transient ischaemic attack within 3 months prior to Screening.
9. Subjects with a pre-existing condition interfering with normal gastrointestinal anatomy or motility, and/or hepatic function that could interfere with the absorption, metabolism, and/or excretion of GSK1278863. Examples of conditions that could interfere with normal gastrointestinal anatomy or motility include gastrointestinal bypass surgery, partial or total gastrectomy, small bowel resection, vagotomy, malabsorption, Crohn's disease, ulcerative colitis, or celiac sprue. Examples of conditions that could interfere with hepatic function include Gilbert's syndrome.
10. Evidence of active peptic, duodenal or esophageal ulcer disease at Screening **OR** history of clinically significant GI bleeding within 3 months prior to Screening.
11. Subjects with chronic inflammatory disease that could impact erythropoiesis (e.g., scleroderma, systemic lupus erythematosus, rheumatoid arthritis, celiac disease).
12. Subjects with a history of symptomatic right heart failure.
13. Subjects with Class III or Class IV heart failure, as defined by the New York Heart Association (NYHA) functional classification system.
14. Active malignancy or diagnosis of malignancy within 5 years prior to Screening (excluding successfully treated basal or squamous cell carcinoma).

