## **6. STUDY ASSESSMENTS AND PROCEDURES**

This section lists the procedures and parameters of each planned study assessment. The exact timing of each assessment is listed in the Time and Events Table Section [6.1](#).

Whenever vital signs, 12-lead ECGs and blood draws are scheduled for the same nominal time, the assessments should occur in the following order:

- 12-lead ECG
- vital signs
- blood draws

The timing of the assessments is required to allow the blood draw to occur as close as possible to the nominal time.

Protocol waivers or exemptions are **not allowed** with the exception of immediate safety concerns. Therefore, adherence to the study design requirements, including those

specified in the Time and Events Table (Section 6.1), are essential and required for study conduct.

The timing and number of planned study assessments and procedures may be altered during the course of the study based on newly available data (e.g., to obtain data closer to the time of peak plasma concentrations) to ensure appropriate monitoring.

The change in timing or addition of time points for any planned study assessments must be approved and documented in a Note to File which is approved by the relevant GSK study team member and then archived in the study sponsor and site study files. This will not constitute a protocol amendment.

The IRB/IEC will be informed of any safety issues that require alteration of the safety monitoring scheme or amendment of the Informed Consent Form (ICF).

Additional safety tests (such as vital signs, physical exams, and clinical laboratory tests) may also be obtained during the course of the study based on newly available data, to ensure appropriate safety monitoring.

**No more than** 500 mL of blood will be collected over the duration of the study, including any extra assessments that may be required.

Refer to [Appendix 3](#) for details regarding PK sample time windows that will not be regarded as protocol deviations.

During the Follow-up Period, deviations of up to +2 days for clinical research unit visits will not be regarded as Protocol Deviations.

The actual date and time will be recorded for all procedures and the Investigator will make every effort to perform procedures at the scheduled nominal dates and times.

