Protein Binding											X d					

- a Both Adverse event monitoring and Concomitant Medication reviews will be conducted throughout the study starting from Day -1.
- b Subjects may remain in residence at the site from the afternoon of Day -1 through the last assessment on Day 17, at the discretion of the investigator or by request of the subject (refer to Section 3.1). Outpatients must return to the site for scheduled PK assessments.
- c Each dose will be administered within 30 min after completion of the night APD treatment or morning last fill of peritoneal dialysis fluid. Outpatients can self administer their daily dose
- d Sampling schedules within the day are given in Section 6.1.1.
- e Sample to be taken predose only.
- f Sample to be taken 24 h post Day 14 dose.
- g Sample to be taken 48 h post Day 14 dose.
- h Sample to be taken 72 h post Day 14 dose.
- i Aliquot of dialysate from the last drained dwell prior to dosing on Day 1. Aliquot for APD subjects may be collected from automated cycler drain/drain bag prior to dosing on Day 1.
- j In CAPD subjects, record volume and take aliquots of dialysate from each drain bag over 24 h dosing period starting at time of Day 14 dose. Aliquot for APD subjects is to be collected from APD collection drain bag over 24 h dosing period starting at time of Day 14 dose.
- k Measurement in addition to clinical chemistry assessment.
- l Measurement in addition to hematology assessment.
- m Test will be performed for drug and alcohol at Screening, Day-1, and Day 13 visits check-in for subjects who participate in the study as outpatient, and it must be negative prior to dosing.
- n Hemoglobin assessment will be by a HemoCue device.

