## 6.3. Safety

Planned timepoints for all safety assessments are listed in the Time and Events Table (Section 6.1).

Additional time points for safety tests such as vital signs, physical exams and laboratory safety tests may be added during the course of the study based on newly available data to ensure appropriate safety monitoring.

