### 6.3.2. Vital Signs

- Vital sign measurements will be measured in supine position **after 5 min** rest and will include systolic and diastolic blood pressure, body temperature, and pulse rate.

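### No blood pressure reading is scheduled on any of the 14 dosing days, so the numeric BP stopping rules cannot stop a subject's own dosing for a symptomless rise unless an unscheduled reading is taken

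*Protocol*

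**What the plan says.** Protocol Section 5.3.3 contains three bullets with numeric BP limits:

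- BP of at least 180/110 mmHg "on a study visit day) which persists for >48 h despite optimal treatment". The same bullet has a clinical part, for hypertension that does not respond adequately to a therapy change.
- BP of at least 160/100 mmHg persisting over 24 h, for subjects with normal baseline BP.
- For subjects with stable elevated baseline BP, a rise of more than 20 mmHg systolic or 10 mmHg diastolic, or a level of 180/110 mmHg or more. Here, "To meet this criterion these elevations must persist longer than 24 h".

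The hemoglobin rules in the same section carry their own schedule. On Days 3, 7 and 11, "hemoglobin will be assessed prior to dosing using a HemoCue device".

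Section 6.3 refers to the Time and Events Table for all planned safety time points. That table marks vital signs at Screening, Day -1, Day 17 and Day 22. Section 6.3.2 ("Vital sign measurements will be measured in supine position", after 5 min rest) includes BP and adds no days. SAP Section 7.4 takes Day -1 as the vital-signs baseline and shows no Day 1 pre-dose collection. Section 6.3 also says: "Additional time points for safety tests such as vital signs, physical exams and laboratory safety tests may be added". Section 5.1 sets once-daily dosing for 14 days, and Time and Events footnote c states: "Outpatients can self administer their daily dose".

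**The concern.** A stopping rule protects a subject only if something measures the quantity while dosing can still be stopped. Each numeric BP rule needs two readings, one that crosses the limit and a later one that shows persistence. The schedule supplies neither during treatment.

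Subjects may enter close to the limit. Exclusion 2 ("Uncontrolled hypertension (diastolic BP" above 100 mmHg, or systolic above 170 mmHg) leaves a subject at 170/100 mmHg eligible. Section 3.3 relies on safety monitoring and stopping criteria to limit risk, and lists stroke, myocardial infarction and heart failure among the events of special interest. Outpatients dosing themselves at home may go several days without seeing site staff.

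The QTc withdrawal criteria in Section 5.3.2 have the same gap: ECGs are scheduled only at Screening, Day -1 and Day 17. The documents name no QT hazard, so that point is secondary.

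**Working it through.** There is no stated figure to reproduce. The check compares the schedule with the rules.

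**Reading the table.** Some rows shifted by one column when the PDF was read. Hemoglobin appears under Day 2, Days 4-6 and Days 8-10, although Section 5.3.3 fixes it at Days 3, 7 and 11. The vital-signs row can be anchored separately: its third mark is in the same column as the third ECG mark, which Section 6.3.3 places on Day 17. To fall on Day 14 it would have to be three columns out.

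**Coverage.**

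- Scheduled BP readings on Days 1-14: 0.
- First dose to next scheduled reading: 17 - 1 = 16 days.
- Last dose to that reading: (17 - 14) x 24 = 72 h.
- Gap between the two post-baseline readings: 22 - 17 = 5 days, both after dosing has ended.
- Doses a numeric BP rule can avert as scheduled: 0.
- Margin between the entry cap and the 180/110 mmHg limit: 180 - 170 = 10 mmHg systolic, and 110 - 100 = 10 mmHg diastolic.

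**Visits during dosing.** Site visits fall on Days 1, 2, 3, 7, 11, 12, 13 and 14. An outpatient has none scheduled on Days 4-6 and 8-10. This treats the marks under those columns as the one-column shift described above. That is established for hemoglobin and inferred for CPK and ALT, whose first three marks sit in the same columns.

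**What added readings could do.** Suppose BP is read before dosing on Days 3, 7, 11, 12 and 13. If a crossing is read on Day d, the repeat falls on Day r = d + 1 (24 h rule) or r = d + 2 (48 h rule). Doses averted are 14 - r + 1 if that morning's dose is held for the repeat, and 14 - r if it was already taken, with a floor of 0.

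| Crossing read on | Repeat just past 24 h | Repeat just past 48 h |
|---|---|---|
| Day 3 | r = 4: 10-11 | r = 5: 9-10 |
| Day 7 | r = 8: 6-7 | r = 9: 5-6 |
| Day 11 | r = 12: 2-3 | r = 13: 1-2 |
| Day 12 | r = 13: 1-2 | r = 14: 0-1 |
| Day 13 | r = 14: 0-1 | r = 15: 0 |

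With no extra visit, the 24 h rule can be checked at the next added BP visit that is clearly past 24 h:

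- Day 3 to Day 7: 14 - 7 + 1 = 8 doses averted.
- Day 7 to Day 11: 14 - 11 + 1 = 4.
- Day 11 to Day 13: 14 - 13 + 1 = 2.

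Added rest time is 5 visits x 5 min = 25 min per subject.

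**The case against.** **The gap is partly covered.** Sections 6 and 6.3 allow extra vital signs, and AE review runs throughout. Section 5.3.3 also lets the investigator stop for significant changes in safety assessments, for symptoms, or for hypertension that does not respond to a therapy change. This stands, and it narrows the gap to symptomless rises. It does not close it, because no added reading is required and a symptomless rise prompts none of these unless BP is taken. Day 17 values could still count toward the study-level rule of three or more subjects.

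**The hazard is not singled out.** Section 3.3 does not name systemic hypertension, reports good tolerability at much higher doses, and the erythropoiesis risk is already monitored by hemoglobin. This is fair as to priority. The protocol nevertheless chose to write three numeric BP rules, and it lists major cardiovascular events as being of special interest.

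**The dose counts are conditional.** They assume a persistent crossing on a given day, and the documents give no probability of one. This is correct: the counts show what the rule could do once triggered, not the expected benefit.

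**Timing is tighter than Section 5.1 suggests.** Section 5.1 allows 2 h from the end of dialysis to dosing on these days, but footnote c allows 30 min for every dose. That inconsistency is real. A 5 min rest fits within either limit, though 30 min is tight for an outpatient who travels in.

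**The change may come too late.** Protocol Section 1.1.1 reports 6 completers against a target of 8, and SAP Section 8 reports 7 enrolled and 5 completed. The counts differ, but both suggest a study near its end. This is the strongest limit on the practical value of the change.

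**Conclusion.** The concern holds. As scheduled, the numeric BP rules in Section 5.3.3 have no reading on any of the 14 dosing days and can avert no dose for a subject with a symptomless rise; the first opportunity to see one is 72 h after the last dose. This applies to inpatients and outpatients alike.

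The conclusion is limited to the numeric rules, the subject's own dosing, and sites that take no unscheduled reading. It rests on the vital-signs row being read correctly, which the ECG row and Section 6.3.3 support. It is a worthwhile, inexpensive correction rather than a defect that undermines the study, and its value depends on whether any subject is still to be dosed.

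**What to change.** - **Section 6.1:** add vital signs before dosing on Days 3, 7, 11, 12 and 13, all visits already attended.
- **Section 5.3.3:** add one sentence requiring a repeat when a BP limit is crossed, just past 24 h, or just past 48 h for the 180/110 mmHg part of the first BP bullet. Each bullet keeps its own persistence period. A subject with stable elevated baseline BP also falls under the third bullet, so for that subject the 24 h repeat applies.
- **Optional ECG:** if an on-treatment ECG is meant to be able to stop dosing, place it on Day 7.

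No threshold changes and no SAP change is needed. The cost is about 25 min of supine rest per subject, plus an occasional unscheduled repeat for an outpatient who crosses a limit on Day 3 or Day 7. Section 6 already sets the order of assessments ("Whenever vital signs, 12-lead ECGs and blood draws are scheduled for the same nominal time"), with vital signs before blood draws. It also allows time points to be added by Note to File without a protocol amendment, so only the sentence in Section 5.3.3 changes protocol text. Aligning footnote c with Section 5.1 on the dosing window at the same time would remove doubt about how long staff have.

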#### **5.4. Blinding**

This will be an open-label study.

#### **5.5. Packaging and Labeling**

The contents of the label will be in accordance with all applicable regulatory requirements.

#### **5.6. Preparation/Handling/Storage/Accountability**

A description of the methods and materials required for preparation of GSK1278863 is provided in [Appendix 5](#).

No special preparation of study treatment is required.

Study treatment will be dispensed or administered according to procedures described herein. Only subjects enrolled in the study will receive study treatment. Only authorized site staff will supply or administer study treatment.

All study treatment must be stored in a secure area with access limited to the investigator and authorized site staff. Study treatment is to be stored to up 30°C (86°F). Maintenance of a temperature log (manual or automated) is required.

The Investigator, institution, or the head of the medical institution (where applicable) is responsible for study treatment accountability, reconciliation, and record maintenance. The Investigator or the head of the medical institution (where applicable), or designated site staff (e.g., storage manager, where applicable) must maintain study treatment accountability records throughout the course of the study. The responsible person(s) will document the amount of study treatment received from and returned to GSK and the amount administered to subjects. The required accountability unit for this study will be tablet. Discrepancies are to be reconciled or resolved. Procedures for final disposition of unused study treatment are listed in the [Appendix 5](#).

GSK1278863 is not expected to pose significant occupational safety risk to site staff under normal conditions of use and administration. Take adequate precautions to avoid direct eye or skin contact.

In the case of unintentional occupational exposure notify the study monitor, GSK Medical Monitor and/or protocol contact.

A Material Safety Data Sheet (MSDS)/equivalent document describing occupational hazards and recommended handling precautions either will be provided to the investigator, where this is required by local laws, or is available upon request from GSK. Precaution will be taken to avoid direct contact with GSK1278863.

## **5.7. Assessment of Compliance**

When the individual dose for a subject is prepared from a bulk supply, the preparation of the dose will be confirmed by a second member of the study site staff.

When subjects are dosed at the study site, they will receive study treatment directly from the Investigator or designee, under medical supervision.

The date and time of each dose administered in the clinic will be recorded in the source documents. The dose of study treatment and study participant identification will be confirmed at the time of dosing by a member of the study site staff other than the person administering the study treatment.

Study site personnel will examine each subject's mouth to ensure that the study treatment was ingested.

## 5.8. Treatment of Study Treatment Overdose

No specific antidote for GSK1278863 is known. The expected manifestations of GSK1278863 overdose include signs and symptoms associated with an excessive and/or rapid increase in Hgb concentration. GSK1278863 is highly protein bound; thus, clearance of GSK1278863 by HD or PD is very low and these are not effective methods to enhance the elimination of GSK1278863. GSK1278863 metabolites are, in part, cleared via hemodialysis.

In the event of suspected overdose:

- collect blood samples for pharmacokinetics and safety laboratory immediately.
- it is recommended that the appropriate supportive clinical care be instituted, as dictated by the subject's clinical status. Additionally, subjects should be monitored closely for CV events, increased heart rate and hematologic abnormalities.

## 5.9. Treatment after the End of the Study

Subjects will not receive any additional treatment from GSK after completion of the study.

The Investigator is responsible for ensuring that consideration has been given to the post-study care of the patient's medical condition, whether or not GSK is providing specific post-study treatment.

## 5.10. Concomitant Medications and Non-Drug Therapies

All concomitant medications (including rhEPO) taken in the 4 weeks before and during the study will be recorded in the eCRF. The minimum requirement is that drug name, dose administered and dates of administration are to be recorded.

*In vitro* characterization of GSK1278863 distribution and biotransformation has identified potential mechanisms for clinical drug-drug interactions. GSK1278863 is primarily metabolized via the CYP2C8 pathway, with minor involvement of the CYP3A4 pathway. Data from a study (PHI113634) to assess the interaction potential between GSK1278863 and a CYP2C8 inhibitor (gemfibrozil) showed a clinically-significant increase in GSK1278863 exposure following co-administration.

*In vitro* studies showed the potential for inhibition of CYP2C8 (IC50: 21 µM) by GSK1278863, while there was no evidence of concentration- or metabolism-dependent inhibitory potential towards human CYP1A2, 2A6, 2B6, 2C9, 2C19, 2D6 or 3A4. In a recent drug-drug interaction, there was no apparent evidence of a drug interaction between GSK1278863, at doses up to 100 mg, with pioglitazone, a CYP2C8 substrate.

GSK1278863 was also observed to be an inhibitor of organic anion transporting polypeptide (OATP) 1B1 and 1B3 *in vitro* with IC50s of ~6 μM and ~11 μM, respectively. The average Cmax observed after single dose administration of 5 mg GSK1278863 to healthy subjects was 0.24 μM, suggesting a low risk of an interaction. In a recent drug-drug interaction, there was no apparent evidence of a drug interaction between GSK1278863, at doses up to 100 mg, with rosuvastatin, an OATP1B1 substrate.

GSK1278863 is a substrate of human breast cancer resistance protein (BCRP) *in vitro*. Therefore, there may be the potential for interactions when GSK1278863 is co-administered with drugs which are inhibitors of human-BCRP, however, GSK1278863 has moderate to high passive permeability, potentially mitigating any BCRP inhibition effects.

